The study population will include pregnant women between the ages 18 and 45 years enrolled as cases and controls. Women at high risk for preeclampsia will be enrolled as cases and those without risk factors for preeclampsia will be approached to serve as a control population. Approximately 250 eligible women will be enrolled in this study (50 in the normal control arm, 100 in the low dose 81 mg per day arm, and 100 in the 162 mg per day arm). Eligible patients will be recruited from UK clinics and the UK Good Samaritan ultrasound unit at the time of their scheduled prenatal visits or ultrasound appointments. Women who plan to deliver at University of Kentucky Chandler Hospital will be approached for enrollment.

The risk factor assessment to screen women at high risk for preeclampsia include:

1. History of preterm preeclampsia, especially when accompanied by an adverse outcome
2. Chronic hypertension
3. Type 1 and Type 2 diabetes
4. Renal diseases
5. Autoimmune disease

Exclusion criteria include:

1. Pregnant women younger than 18 years or older than 45 years
2. Multiple gestations
3. History of allergy (urticaria or anaphylaxis) to aspirin or aspirin related products asthma that worsens after aspirin use
4. Patients with gastrointestinal or genitourinary bleeding
5. Patients with peptic ulcer disease
6. Patients with severe liver dysfunction
7. Patients who have undergone bypass surgery
8. Patients on anticoagulant medication(s)
9. Women with anomalous fetus

Recruitment and data collection is expected to last throughout 2018-2022 academic years. Data analysis is expected to be accomplished during 2019-2022 academic years.

Attachments

Indicate the targeted/planned enrollment of the following members of minority groups and their subpopulations. Possible demographic sources: [Census Regional Analyst Edition](#), [Kentucky Race/Ethnic Table](#), [Kentucky Population Data](#).

(Please note: The IRB will expect this information to be reported at Continuation Review time for Pre-2019 FDA-regulated Expedited review and Full review applications):

Participant Demographics

	Cisgender Man 	Cisgender Woman 	TGNB/TGE 	Unknown/Not Reported
American Indian/Alaskan Native:	0	2		
Asian:	0	10		
Black/African American:	0	35		
Latinx:	0	25		
Native Hawaiian/Pacific Islander:	0	2		
White:	0	166		
American Arab/Middle Eastern/North African:		1		
Indigenous People Around		1		

the World: _____

More than One Race:	8		
Unknown or Not Reported:	0	0	

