Aspirin pharmacokinetics have been studied in pregnancy. The metabolism of aspirin is altered in pregnancy due to physiological changes in gastrointestinal absorption, accumulation in body fat and decreased drug binding to plasma proteins and changes in renal excretion due to increase renal plasma flow and glomerular filtration rate. Jacobson and colleagues investigated the transfer of acetylsalicylic acid in a perfused human placental cotyledon and its effects on fetal placental unit. When isolated perfused human cotyledons were treated with acetyl salicylic acid, 60% of acetyl salicylic acid was extracted from the maternal perfusate when steady state was reached and less than 15% was noted in the fetal circulation. These levels were much lower than those known to inhibit thromboxane or alter fetal perfusion pressure. The much lower concentrations seen in the fetal circulation than what is extracted from the maternal perfusate might be presumably due to placental metabolism. Jacobson, R. L., Brewer, A., Eis, A., Siddiqi, T. A., & Myatt, L. (1991). Transfer of aspirin across the perfused human placental cotyledon. *American Journal of Obstetrics & Gynecology*, 165(4), 939-944.

Although this intervention is well supported and low risk, aspirin has several pharmacokinetic mechanisms of action and the way it modifies disease in some pregnant patients is unclear⁵. Aspirin triggered lipoxins (ATL/LXA4) are lipid mediators produced from arachidonic acid that are thought to work through anti-oxidant and anti-inflammatory roles to result in tissue specific, and possibly, systemic change. These mediators occur naturally but are increased by aspirin administration and pregnant mouse models show reduction of pre-eclamptic disease with administration⁶. Further, a cohort study of pregnant women showed lower circulating levels of ATL/LXA4 and placental receptor (ALX) expression in pre-eclamptic women⁷. As pre-eclampsia is a disease of widespread endothelial damage and inflammation triggered by placental dysfunction, we surmise that aspirin's effectiveness as a prophylactic therapy could be through alteration of ATL/LXA4 and receptor (ALX) expression at the placental level.

The pharmacokinetics of aspirin in pregnancy has not been clearly defined and existing sparse data from animal and some human placental models therefore supports the construct that the efficacy of the intervention may be dependent upon dose and volume of distribution.

Objectives

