List your research objectives. Please include a summary of intended research objectives in the box below.

The objective of our study is to determine if low dose aspirin has a dose dependent response to modify maternal endothelial dysfunction and impedance in uterine arteries when used in the prophylaxis of preeclampsia prevention in women identified as at high risk for development of preeclampsia.

Another objective of our current study is to understand the important mechanism of prevention of pre-eclampsia with the ultimate goal to improve targeting of therapy to pregnant women who will benefit from aspirin exposure in pregnancy. We will accomplish this by evaluating ATL/LXA4 concentrations as a mechanism of aspirin benefit.

Study Design

Describe and explain the study design (e.g., observational, secondary analysis, single/double blind, parallel, crossover, deception, etc.).

- **Clinical Research:** Indicate whether subjects will be randomized and whether subjects will receive any placebo.
- **Community-Based Participatory Research:** If you are conducting [community-based participatory research \(CBPR\)](#), describe strategies for involvement of community members in the design and implementation of the study, and dissemination of results from the study.
- **Qualitative research:** Indicate ranges where flexibility is needed, if a fixed interview transcript is not available, describe interview topics including the most sensitive potential questions.
- **Research Repositories:** If the purpose of this submission is to establish a Research Repository (bank, registry) and the material you plan to collect is already available from a commercial supplier, clinical lab, or established IRB approved research repository, provide scientific justification for establishing an additional repository collecting duplicate material. Describe the repository design and operating procedures. For relevant information to include, see the [UK Research Biospecimen Bank Guidance](#) or the [UK Research Registry Guidance](#).

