This is a single center, prospective, randomized, open-label clinical trial. The experimental group will include pregnant women who are identified at high risk for preeclampsia either by history, presence of risk factors, or abnormal uterine artery Doppler impedance. They will be divided into two groups based on their body mass index (BMI) (<30 and =30). Patients in each group will be randomized to receive either aspirin 81 mg (1 tablet of baby aspirin) or aspirin 162 mg (2 tablets of baby aspirin) daily initiated between 11 and 16 weeks of gestation and continued until 36 weeks of gestation. There will be a third control group of pregnant women at low risk for preeclampsia based on their risk factor assessment to provide baseline data. The control group will not receive aspirin. Both of the experimental and control groups will be assessed with uterine artery Doppler studies and FMD of the brachial artery at three different time points in pregnancy: at enrollment between 11 and 16 weeks, between 18 and 22 weeks (+/- 7 days), and between 28 and 32 weeks of gestation(+/- 7 days). We will obtain baseline blood and urine samples at the time of enrollment and later between 28 and 32 weeks (+/- 7 days) to assess salicylate levels, thromboxane and endothelin-1 levels. We will also obtain cord blood and placental samples from the experimental and control population at the time of delivery.

Attachments

Subject Recruitment Methods & Advertising

Describe how the study team will identify and recruit subjects. Please consider the following items and provide additional information as needed so that the IRB can follow each step of the recruitment process.

- How will the study team identify potential participants?
- Who will first contact the potential subjects, and how?
- Will you use advertisements? If so, how will you distribute those?
- How and where will the research team meet with potential participants?
- If applicable, describe proposed outreach programs for recruiting women, minorities, or disparate populations.
- How you will minimize undue influence in recruitment?
- Attach copies of all recruiting and advertising materials (emails, verbal scripts, flyers, posts, messages, etc.).

For additional information on recruiting and advertising:

- [IRB Application Instructions - Advertisements](#)
- [PI Guide to Identification and Recruitment of Human Subjects for Research](#)

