The research procedures including patient enrollment will happen at the time of their routine prenatal visits and no additional visits for the purpose of this research are anticipated. The procedures patients will undergo during their visits and the timeline are shown in the attached table. The experimental group will include pregnant women who are identified at high risk for preeclampsia either by history, presence of risk factors, or abnormal uterine artery Doppler impedance. They will be divided into two groups based on their body mass index (BMI) (<30 and >=30). Patients in each group will be randomized to receive either aspirin 81 mg (1 tablet of baby aspirin) or aspirin 162 mg (2 tablets of baby aspirin) daily initiated between 11 and 16 weeks of gestation and continued until 36 weeks of gestation. There will be a third control group of pregnant women at low risk for preeclampsia based on their risk factor assessment to provide baseline data. The control group will not receive any aspirin.

After their initial enrollment, patients in the experimental group will be divided into 2 groups based on their body mass index (BMI) : <30 and >=30. Patients in each group will be randomized to receive aspirin 81 mg(1 low-dose aspirin tablet) or aspirin 162 mg (2 low dose aspirin tablets per day) daily until 36 weeks of gestation. Prescribing low dose aspirin is part of the standard prenatal care for women who are identified as at high risk for preeclampsia.

The prescription for aspirin for the patients enrolled in the study will be sent to the UK Good Samaritan Hospital outpatient pharmacy. When patients are randomized to Aspirin 162 mg (2 tablets of baby aspirin) and there is an additional cost to the patient due to the higher dose. The Division of Maternal Fetal Medicine at UK will receive a monthly statement from UK Good Samaritan Hospital pharmacy for every dose of 162mg that was filled during the previous month.

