Inserted	1031173	104560	10446600	SP	N	[name]	[contact]						N	Data Analysis/Processing		P	N	ash231	4/28/2025 10:06:22 AM	N			

Modification Comment by [name] - ORI to PI on 4/28/2025 10:13:11 AM
Please add the changes being made to "[name]" - highlighted in study personnel section but not included here.

Statistical Analysis Plan NCT03893630 6/27/2025

To begin, continuous variables (age, BMI, gestational age at delivery, etc.) will be summarized with descriptive statistics (n, mean, standard error); categorical variables (e.g., pre-eclampsia, method of conception, etc.) will be summarized with counts and percentages.

The primary outcome, difference in uterine artery pulsatility index (PI) will be calculated as the difference in PI for each patient between each trimester visit. PI at each visit will be calculated by averaging left-side and right-side PIs from each of three (or all available) images on each side for each patient using ultrasound technology. For a very limited number of images identified using clinical expertise, the MATLAB code below will be used to produce PI values if ultrasound technology is insufficient.

An independent and automated image analysis pipeline will be developed using R to crop images and MATLAB to perform image analysis. For each available ultrasound image, an estimated mean PI will be calculated as the average of the PI from each analyzable waveform. For each patient at each visit, left- and right-side estimates will be obtained using the median of the available image-level estimates, since the median is more robust to outliers resulting from images that might be difficult to read. Finally, the mean PI for each patient at each visit will be calculated using the average of the left- and right-side estimates. Means and SDs of these indices will be compared to (1) ensure that there are no drastic differences from the values calculated using the ultrasound technology and the alternative pipeline, and (2) demonstrate the robustness of the calculated primary outcome values.

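### Women are randomised to 81 or 162 mg within BMI <30 and >=30, but the SAP gives that stratum no role in analysis and states no dose comparison in which it could be used

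*Combined protocol and SAP*

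**What the plan says.** **Rationale.** The last paragraph of the Background, before Objectives, says that the sparse data from animal and human placental models "supports the construct that the efficacy of the intervention may be dependent upon dose and volume of distribution". The same part of the Background lists "accumulation in body fat and decreased drug binding to plasma proteins" among the changes of pregnancy that alter aspirin metabolism.

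**Objective.** The first objective is to "determine if low dose aspirin has a dose dependent response to modify maternal endothelial dysfunction and impedance in uterine arteries" in high-risk women. BMI is not mentioned.

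**Randomisation.** Research Procedures states that "patients in the experimental group will be divided into 2 groups based on their body mass index (BMI) : <30 and >=30". Study Design adds: "Patients in each group will be randomized to receive either aspirin 81 mg (1 tablet of baby aspirin) or aspirin 162 mg". The Subject Demographics section plans "100 in the low dose 81 mg per day arm, and 100 in the 162 mg per day arm", plus 50 untreated low-risk controls.

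**SAP.** BMI appears once: "continuous variables (age, BMI, gestational age at delivery, etc.) will be summarized with descriptive statistics (n, mean, standard error". The <30 and >=30 groups do not appear. The SAP defines the primary outcome as each patient's change in uterine artery pulsatility index (PI) between visits and explains how PI is obtained from the images. The only comparison it names is between PI from the ultrasound machine and PI from the automated image pipeline. It gives no test or model for 162 versus 81 mg, and it does not mention FMD.

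**The concern.** BMI group is the only stratification factor described. A factor used to constrain the allocation would normally be carried into the comparison that the allocation supports. Here it is not, and the comparison itself is unwritten.

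Two things are at stake. The first is precision. If BMI group predicts PI change or FMD and is left out of the model, variation between the strata goes into the error term, although balanced stratified allocation has already removed it from the treatment contrast. The interval is then wider than it need be.

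The second is prespecification. The trial is open-label and the SAP is dated 6/27/2025. Without a written rule, whether to adjust for BMI and whether to show results by BMI group could both be settled after the data have been seen. That matters for a plan whose rationale mentions volume of distribution and whose doses are fixed in milligrams, because readers will ask whether the dose effect differs with body size.

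**Working it through.** The documents give no alpha, power, effect size, SD or sample-size derivation, so there is no stated figure to reproduce. The planned numbers do add up: 50 + 100 + 100 = 250.

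**Inputs from the documents:** 100 women per aspirin arm; strata BMI <30 and >=30; two doses randomised within each stratum.

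**Assumed inputs:** two-sided alpha 0.05; 80% power; outcomes in SD units (within-stratum SD = 1); half of each arm with BMI >=30 unless stated; exact balance of the arms within strata.

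**1. Overall dose difference detectable.** (1.960 + 0.842) × √(2/100) = 2.802 × 0.1414 = 0.40 SD.

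**2. Cost of leaving the stratum out.** Let BMI group shift the outcome by *b* SD. With balanced strata, the true variance of the dose difference stays at 2/100. An unadjusted test estimates the outcome variance as about 1 + *b*²/4, so its critical value is in effect 1.960 × √(1 + *b*²/4). Power at 0.40 SD is Φ(0.40/√0.02 − that value), where 0.40/√0.02 = 2.828. A simulation with 20,000 runs per scenario gave:

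| Shift *b* | Effective critical value | Type I error, formula | Type I error, simulated | Power, formula | Power unadjusted, simulated | Power adjusted, simulated |
|---|---|---|---|---|---|---|
| 0 | 1.960 | 5.0% | 5.2% | 81% | 81% | 81% |
| 0.5 SD | 2.020 | 4.3% | 4.4% | 79% | 78% | 80% |
| 1 SD | 2.191 | 2.8% | 3.0% | 74% | 73% | 80% |

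The stratum-adjusted test kept a type I error of 5.1 to 5.2% throughout. So omitting the stratum makes the test conservative, not biased, and costs nothing if BMI group does not predict the outcome.

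**3. What can be learned by BMI group.** Within one stratum of 50 per arm, the detectable difference is 2.802 × √(2/50) = 0.56 SD. If 30% of women are in one stratum, it is 2.802 × √(2/30) = 0.72 SD there and 2.802 × √(2/70) = 0.47 SD in the other.

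For the dose-by-BMI-group interaction:
- 50:50 split: 2.802 × √(2/50 + 2/50) = 0.79 SD
- 30:70 split: 2.802 × √(2/30 + 2/70) = 0.87 SD (0.865 before rounding)

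Power for an interaction of 0.40 SD is only 25 to 29% over these splits.

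**4. Sensitivity to the sample size.** Project Information gives a maximum of 209 subjects. If 50 are controls, (209 − 50)/2 = 79.5 remain per aspirin arm. The detectable overall difference is then 0.44 SD and the detectable interaction 0.89 to 0.97 SD.

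**5. Illustration of dose by body size.** At an assumed height of 1.63 m, weight is BMI × 1.63²: 58.5 kg at BMI 22 and 106.3 kg at BMI 40. Then 81/58.5 = 1.39 mg/kg and 162/106.3 = 1.52 mg/kg, so dose per kg can overlap between the arms. Height and both BMI values are chosen for illustration; the documents give neither the trial's BMI distribution nor any per-kg reasoning.

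**The case against.** The strongest objection is that one cannot fault the covariates of a model that has not been written. The SAP as supplied contains no 162 versus 81 mg contrast, pooled or otherwise, so the larger gap is the missing comparison and stratum adjustment is a detail of filling it. This stands, and the point is framed accordingly. The SAP also refers to MATLAB code that is not in the supplied text, so the absence is asserted for that text only.

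A reader might infer that the BMI split was built to test the volume-of-distribution idea. The documents do not say so. No section explains why BMI was chosen. The Background discusses volume of distribution in a maternal-fetal compartment model, and body fat is listed as one pharmacokinetic factor without being tied to the split. Balancing the arms is an equally good reading.

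A reader might also infer that the dose-dependence objective goes unanswered without a BMI analysis. It does not: the objective does not mention BMI, and a randomised 162 versus 81 mg comparison would answer it on average. If the effect lay in only one of two equal strata, the pooled difference would be half of it, but that describes an average effect and does not invalidate the comparison.

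It is also fair to say that the precision loss may be nil. The primary outcome is a within-patient change, which removes constant BMI-related differences in PI level, and no figure in the documents shows that BMI group predicts PI change or FMD. The salicylate and thromboxane measurements already planned are more direct measures of exposure and response than a cut at BMI 30. None of this argues against including the stratum; it limits how much is lost without it.

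**Conclusion.** The point holds in a limited form. The trial randomises within two BMI groups, and the supplied SAP neither uses those groups nor states the dose comparison to which they belong. An unadjusted comparison would be unbiased for the average dose effect. Its cost runs from nothing, if BMI group does not shift the outcome, to about 7 percentage points of power (80% to 73%) with a type I error near 3%, if the shift is 1 SD. The loss is about 2 points at 0.5 SD.

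These figures rest on assumed alpha, power, effect size, stratum split and BMI shift, and on allocation balanced within strata. The documents do not describe the method, such as blocking, that would secure that balance. With simple randomisation inside each stratum, the unadjusted test would keep its 5% level but would still lose power.

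The design cannot settle whether the dose effect differs by BMI group unless that difference is very large, roughly 0.8 to 0.9 SD.

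**What to change.** In the SAP:

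1. State the 162 versus 81 mg comparison for PI change and for FMD, with the BMI randomisation group (<30, >=30) as a factor in the model.
2. As exploratory only, report the 162 minus 81 mg difference with its confidence interval in each BMI group, and the dose-by-BMI-group estimate with its interval.
3. Say beside those results that about 100 women per arm can detect only an interaction of roughly 0.8 to 0.9 SD (two-sided alpha 0.05, 80% power, SD units), so a null interaction is not evidence that the effect is the same in both groups.

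The cost is a few sentences in the SAP and one extra term in the main model. BMI group is already known for every randomised woman, so no new data are needed. The drawback is that the intervals within BMI groups will be wide and open to over-reading, hence the exploratory label.

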Participants will be recruited from UK Polk Dalton clinic, Good Samaritan Obstetrics and Gynecology clinic, and the Good Samaritan Ultrasound unit. Patients will be greeted in person and recruitment will be done in a private room. Study personnel who work in the clinics listed above with access to patients' identity and information will be involved in patient recruitment and consenting processes. Recruitment of Hispanic patients will be accomplished by certified Spanish translators identified as support staff under study personnel who will be present onsite. The initial recruitment process will not involve any Hispanic patients until a modification is submitted to the IRB with a detailed Spanish consent. The recruitment of the Hispanic patients will begin after the consent form in Spanish has been approved by the IRB.

There will be no advertising.

Attachments

Research Procedures

Describe how the research will be conducted.

- What experience will study participants have?
- What will study participants be expected to do?
- How long will the study last?
- Outline the schedule and timing of study procedures.
- Provide visit-by-visit listing of all procedures that will take place.
- Identify all procedures that will be carried out with each group of participants.
- Describe deception and debrief procedures if deception is involved.

Differentiate between procedures that involve standard/routine clinical care and those that will be performed specifically for this research project. List medications that are explicitly forbidden or permitted during study participation.

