Patients in both the experimental and control groups will undergo two sets of ultrasound assessments - uterine and brachial arteries, during their routine prenatal ultrasound evaluation at different time points in their pregnancy at UK Good Samaritan hospital. Initial assessment would be during their initial enrollment less than 16 weeks of gestation. The other two would be between 20 and 22 weeks (+/- 7 days) and between 28 and 32 (+/- 7 days) weeks during their routine ultrasound evaluation for fetal anatomy and fetal growth respectively. During their ultrasound visit, after completion of their routine evaluation indicated for that visit, doppler assessment of the uterine arteries will be done. Following this, Doppler assessment of the brachial artery will be performed known as the flow mediated dilation (FMD).

The baseline diameter of the brachial artery will be first recorded using the ultrasound transducer probe. Thereafter a blood pressure cuff will be placed around the forearm distal to the ultrasound probe and inflated to 25-50 mm Hg above the systolic arterial pressure for 5 minutes to elicit a reactive hyperemic stimulus. The cuff will then be deflated and the longitudinal image of the brachial artery will be obtained continuously from 30 seconds before and 2 minutes after the cuff deflation. Flow mediated dilation will be calculated using the following equation: FMD (%) = (Peak diameter - Baseline diameter) / Baseline diameter

Patients will also provide an extra tube of blood and urine specimen collected during their routine prenatal laboratory evaluation performed at the time of first trimester screening and for gestational diabetes screening in the late second/early third trimester. Finally, cord blood and will be collected in 15 patients from each group to assess whether the variation in dose results in appreciably greater fetal cord blood concentrations. The first 15 deliveries from each group in the study will be selected for cord blood and placental collection at the time of delivery. Medical records will be abstracted to collect demographic information, medical and prenatal history, treatment course, ultrasound information, information related to delivery and neonate after birth (Birth weight, gender, APGARS and neonatal complications).

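### Sampling cord blood and placenta from the first 15 deliveries per group lets gestation at delivery help choose the subset; the tilt is small over 2018-2022 recruitment, but avoidable and uncorrected

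*Combined protocol and SAP*

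**What the plan says.** - **Who is sampled.** Research Procedures says: "The first 15 deliveries from each group in the study will be selected for cord blood and placental collection at the time of delivery". The sentence before it gives the size and purpose: cord blood is to be "collected in 15 patients from each group to assess whether the variation in dose results in appreciably greater fetal cord blood concentrations". No power, effect size or SD is given for the 15.
- **Study Design** describes the same collection without the limit: "We will also obtain cord blood and placental samples from the experimental and control population at the time of delivery".
- **Why placenta.** The background section surmises that aspirin may work through "alteration of ATL/LXA4 and receptor (ALX) expression at the placental level". It also cites lower circulating ATL/LXA4 and lower placental ALX expression in preeclamptic women. Objectives lists ATL/LXA4 as a mechanism to be evaluated.
- **Arms and timing.** The study population description plans "50 in the normal control arm, 100 in the low dose 81 mg per day arm, and 100 in the 162 mg per day arm" and says "Recruitment and data collection is expected to last throughout 2018-2022 academic years". Study Design has aspirin taken "daily initiated between 11 and 16 weeks of gestation and continued until 36 weeks of gestation".
- **Analysis.** The SAP covers descriptive summaries and the uterine artery pulsatility index. It names no cord or placental analysis and no adjustment for gestation at delivery.

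**The concern.** Counting deliveries, not randomisations, lets part of the outcome choose the sample. Of two women enrolled in the same week at the same gestation, the one who delivers at 30 weeks enters the subset ahead of the one who delivers at 39.

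Early delivery is linked to preterm preeclampsia, which aspirin is given to prevent. On the protocol's own background it is also plausibly linked to the placental markers. It is linked to cord concentrations too: dosing is planned to end at 36 weeks, so a woman who delivers earlier may still be taking aspirin while a later one has stopped. A comparison between doses in subsets chosen this way does not inherit the full protection of randomisation, and the subset need not represent its arm.

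**Working it through.** **The plan's own figure.** The 15 per group comes with no inputs, so it cannot be reproduced. What can be checked is how far the rule tilts the subset.

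**Inputs from the documents.** N = 100 per aspirin arm; recruitment over about four years (T = 208 weeks); enrolment at 11-16 weeks; subset k = 15.

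**Assumptions, not in the documents.** Even accrual; preterm (<37 weeks) rate p = 25%, range 15-35%; and Δ, the difference in mean gestation between term and preterm deliveries. Two distributions were tried:

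- Late-weighted: preterm at 37 weeks minus an exponential of mean 2.5 (mean 34.5), term mean 39. Δ = 4.5 weeks.
- Spread: preterm uniform 27-37 (mean 32), term uniform 37-40.5 (mean 38.75). Δ = 6.75 weeks.

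**Formula.** Delivery date = enrolment date + (gestation at delivery − gestation at enrolment). Enrolling 15 women takes W = 15T/N weeks. With even entry, preterm women have on average Δ more weeks of enrolment dates that fall inside the counting window. Approximately:

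preterm share of first 15 = p × [1 + (1 − p)Δ/W]

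For four years, W = 15 × 208/100 = 31.2 weeks:

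- Δ = 4.5: 0.25 × (1 + 0.75 × 4.5/31.2) = 27.7%
- Δ = 6.75: 0.25 × (1 + 0.75 × 6.75/31.2) = 29.1%

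Monte Carlo runs (6,000 per case for Δ = 4.5; 4,000 for Δ = 6.75) agree:

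| Recruitment | W (weeks) | Δ = 4.5: formula / simulated | Δ = 6.75: formula / simulated |
|---|---|---|---|
| 48 months | 31.2 | 27.7% / 27.7% | 29.1% / 29% |
| 24 months | 15.6 | 30.4% / 30.5% | 33.1% / 33% |
| 12 months | 7.8 | 35.8% / 35.9% | 41.2% / 41% |

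Taking the first 15 enrolled gives 25% in every row.

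**In women.** At 48 months the excess is 15 × (0.277 − 0.25) = 0.4 to 15 × (0.291 − 0.25) = 0.6 of a woman. At 12 months it is 15 × (0.358 − 0.25) = 1.6 to 15 × (0.412 − 0.25) = 2.4.

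**Other preterm rates.** At 48 months, a true 15% becomes 16.8-18% and a true 35% becomes 38.4-40%. At 12 months they become 22.4-26% and 48-55%.

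**Why it is small over four years.** About 96% of the first 15 to deliver are also among the first 15 enrolled (85% at 12 months). Mean gestation at delivery is 37.7 weeks in the subset against 37.9 in the arm (Δ = 4.5).

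**Effect on the dose contrast.** If the two doses produced the same distribution of gestation at delivery and accrued in parallel, both subsets would tilt equally. If true preterm rates were 30% and 20%, the 48-month subsets would show 32.9% against 22.5% (Δ = 4.5) or about 34.5% against 23.5% (Δ = 6.75). The 10-point gap grows by 0.4 to 1 point. At 12 months with Δ = 4.5 it is 42.1% against 29.2%, a growth of 2.9 points. If preterm delivery shifted a marker by 1 SD (assumed), one extra point adds 0.01 SD. For scale, 15 per arm has 80% power only for (1.96 + 0.84) × √(2/15) = 1.02 SD.

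**The case against.** The strongest reply is that, with staggered entry, the order of delivery is mostly the order of enrolment, which precedes treatment. That stands, and it is why the excess is about half a woman in 15. The larger figures need accrual of about a year, or front-loaded accrual, which the documents do not state. It also stands that the SAP specifies no cord or placental test, so no prespecified test is biased, and that maternal blood and urine are collected without the limit of 15.

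Three stronger readings are tempting and are not supported:

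- **That the subset would consist largely of preterm deliveries or failures of prophylaxis.** On the stated schedule the composition barely moves.
- **That the rule causes the confounding in the contrast with controls.** Controls are low-risk, untreated and not randomised. They differ from the aspirin arms in disease and gestation under any sampling rule.
- **That Study Design promises samples from every woman.** It states no limit, but it does not say all women, and Research Procedures can be read as its detail. This needs clarifying; it is not a proven contradiction.

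The reply does not remove the dependence on delivery timing, which runs in the same direction in every scenario and which no part of the plan addresses.

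**Conclusion.** The concern holds as a small, avoidable selection effect. The rule makes membership depend partly on a post-randomisation outcome and tilts the samples used to compare doses towards early deliveries. Under even recruitment over about four years and an assumed 25% preterm rate, the size is 0.4-0.6 extra preterm women in 15, and a between-dose gap in preterm share that widens by a point or less. It becomes material, at roughly 1.6 to 2.4 women in 15, only if accrual took about 12 months. Neither the preterm rate nor the actual accrual pattern is in the documents, so the direction is firm and the size is conditional. The case for changing the rule is that the change costs almost nothing.

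**What to change.** **If collection is still open.** Define the subset as the first 15 women per arm by randomisation number, and by enrolment order for controls, fixed before delivery. State how the 15 are split across the two BMI strata, since 15 does not divide evenly. Record every selected woman who is missed, with her gestation at delivery and the reason. Replacing missed women can itself bring selection back if unplanned early deliveries are missed more often. The number of samples and assays is unchanged; the delivery unit needs a list of flagged study numbers in place of a running count.

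**If samples are already collected.** This is plausible, given planned recruitment to 2022 and a SAP dated June 2025. Report gestation at delivery for each subset against its full arm. Adjust the between-dose cord and placental comparison for it, using the delivery data already abstracted under Research Procedures. Show the unadjusted result alongside, because gestation at delivery is itself post-randomisation. Do not describe the comparison as protected by randomisation. Where it was recorded, report time since last aspirin dose for the cord samples, since this varies with gestation at delivery under either rule. The cost is a few lines in the SAP.

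**In both cases.** Reconcile Study Design with Research Procedures on the limit of 15, and state that group means treatment arm, because Research Procedures also uses the word for the BMI strata. Note one limit that the new rule does not remove: "The initial recruitment process will not involve any Hispanic patients until a modification is submitted to the IRB with a detailed Spanish consent". The earliest women under either rule may therefore include no Hispanic participants, and the subset's make-up should be reported.
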